8.1.4. Long-term outcomes and Future research

We will collect long-term outcome data beyond the end of the 12-month active study participation period. We will passively monitor care through the electronic medical record in order to identify and track problems with organ function or other health problems that may develop, related to the transplant and study participation. This data will be stored safely like all other data, with all necessary precautions.

Subjects will also be approached to provide optional blood sample for testing of viral kinetics (HCV RNA), donor and recipient IL-28B polymorphisms, and alloimmune responses (T- and B-cell function). Samples will be stored in a locked freezer, using encrypted patient IDs.

De-identified samples from subjects may be sent to other investigators for their research. These samples may include information such as sex, age, health history, or ethnicity. These samples will not be sold. Some future studies may need health information (such as smoking history or present health status) that may require contacting the subject to obtain.

8.2. Study schedule of procedures

8.2.1. Visits, lab testing, and other clinical testing

See next page for table.

Transplanting HCV Lungs into HCV Negative Lung Recipients

Protocol V5.0, November 2020

Week(s) post-KT		Day(s) post-KT		Visit Schedule		Research Visit Activities					Research Labs					Standard of Care								
Week(s) post-KT	Day(s) post-KT	Visit	Study Visits	Lab-Only	Informed Consent	Assess Adverse Events	Current Medications	Fibroscan	RAND-36 Questionnaire	HBV DNA HIV AB & LFTs	HBV Core Antibody	Urine Preg Test	Urine Protein/Cre Ratio	HCV RNA	Viral Kinetics (optional)♦	NSSA Resistance**	Genotyping of donor and/or recipient	Vitals & Physical Exam	Surveillance biopsy	CMP*	CBC	Tacrolimus		
Screening					✓	✓	✓	✓	✓	✓	✓	✓	✓	✓				✓						
1 (Begin treatment)	Day 2 - 7	V1	✓			✓	✓				✓■			✓	✓	✓	✓	✓	✓	✓	✓	✓		
1	7 ± 1 day			✓			✓							✓	✓					✓	✓	✓	✓	
2	10 ± 1 day	V2	✓			✓	✓							✓	✓				✓	✓	✓	✓	✓	
2	14 ± 1 day			✓			✓							✓	✓				¥	✓	✓	✓	✓	
3	21 ± 3 day	V3	✓			✓	✓							✓	✓				✓	✓	✓	✓	✓	
4	28 ± 3 day	V4	✓			✓	✓	✓	✓					✓	✓	✓			✓	✓	✓	✓	✓	
6	42 ± 7 day	V5	✓			✓	✓				✓■			✓	✓				✓	✓	✓	✓	✓	
8	56 ± 7 day	V6	✓			✓	✓							✓	✓				✓	✓	✓	✓	✓	
10	70 ± 7 day	V7	✓			✓	✓								✓				✓	✓	✓	✓	✓	
12	84 ± 7 day	V8	✓			✓	✓				✓■			✓	✓	✓			✓	✓	✓	✓	✓	
13 (End treatment)†	91 ± 7 day			✓			✓								✓									
16 (SVR 4)†	112 ± 14 day	V9	✓†			✓	✓							✓	✓			✓†	✓	✓	✓	✓	✓	
20 (SVR 8)	140 ± 7 day			✓										✓	✓				✓	✓	✓	✓	✓	
24 (SVR 12)	168 ± 14 day	V10	✓			✓		✓	✓					✓	✓	✓			✓	✓	✓	✓	✓	
28†	196 ± 7 day			✓											✓					✓	✓	✓	✓	✓
32	224 ± 7 day			✓											✓					✓	✓	✓	✓	✓
36 (SVR 24)	252 ± 7 day			✓										✓	✓	✓			✓	✓	✓	✓	✓	
40	280 ± 14 day			✓										✓					✓	✓	✓	✓	✓	
52	365 ± 14 day	V11	✓			✓		✓	✓					✓	✓	✓			✓	✓	✓	✓	✓	

* CMP=comprehensive metabolic panel which includes basic metabolic panel and liver function tests
care blood draw

** As appropriate ♦Viral Kinetics testing can be done anytime there is a standard of

[†]If patients require the 16 weeks of therapy, the last 4 weeks would be the same as weeks 9-12 of therapy [■]Only if HBV Core Antibodies are positive.

8.2.2. Blood sampling volumes

Maximum Post-Transplant Blood Draw Totals								
Week Post-KT	CBC	CMP	Tacrolimus/ Cyclosporine	HBV Core Antibody	HCV RNA	Viral Kinetics (optional)♦	NS5A Resistance	Blood Draw Total
1	4	4.5	4	4	6	6	2	28.5
1	4	4.5	4	0	6	6	0	24.5
2	4	4.5	4	0	6	6	0	24.5
2	4	4.5	4	0	6	6	0	24.5
3	4	4.5	4	0	6	6	0	24.5
4	4	4.5	4	0	6	6	0	18.5
6	4	4.5	4	4	6	6	0	24.5
8	4	4.5	4	0	6	6	0	24.5
10	4	4.5	4	0	0	6	0	18.5
12	4	4.5	4	4	6	6	0	28.5
16	4	4.5	4	0	6	6	0	24.5
20	4	4.5	4	0	6	6	0	24.5
24	4	4.5	4	0	6	6	0	24.5
28	4	4.5	4	0	0	6	0	18.5
36	4	4.5	4	0	6	6	0	24.5
40	4	4.5	4	0	0	6	0	18.5
52	4	4.5	4	0	6	6	0	24.5
Total	68	76.5	68	0	84	102	2	400.5

♦ Lung transplant recipients have twice a week labs including tacrolimus or cyclosporine levels, CBC and a CMP after discharge for the first 6-8 weeks

♦ There may also be additional blood draws due to optional Viral Kinetics lab testing increasing the total sample volume.

8.3. Subject retention and drug adherence

We will enforce subject retention in several ways. We will record extensive contact information for each subject at their enrollment in the trial. This will include home, work, and cellular telephone numbers. The research staff will call before each study visit to remind the subject to attend. We will also obtain contact information of a family member or friend so that we can contact him/her if the subject does not answer his/her regular phone number.

An adequate record of receipt, distribution, and return of all study drugs must be kept. Subject adherence with the treatment and protocol includes willingness to comply with all aspects of the protocol, and to have blood collected for all safety evaluations.

The research staff and physician will explain the importance of adherence with the study protocol at each subject contact. If a subject fails to comply with a study visit, the staff will contact him or her by telephone. If this fails, the staff will send two certified express letters one week apart, to request follow-up.

We have considered how to minimize non-adherence with therapy. We will strongly emphasize the importance of complying with the study drug treatment. Nonetheless, we will perform pill counts at visits and record episodes when medication is withheld for any reason. If a subject has a serious adverse event (SAE) (whether

related to study drugs or not), we will continue to follow-up with the subject for study assessments to assist with safety monitoring and to avoid the problems introduced by missing data. The inclusion of such follow-up data will allow for analysis by intention-to-treat. If a study subject withdraws consent, he/she will no longer be followed.

9 CHAPTER 6: ASSESSMENT OF EFFICACY AND OUTCOME MEASURES

9.1. Assessments of Efficacy

The primary aims of the study are to determine sustained virologic response rates (SVR) of open-label Zepatier, Epclusa, or another appropriate antiviral treatment administered to HCV-negative patients with lung failure who receive a lung transplant from an HCV-infected donor, leading to post-transplant de-novo HCV infection.

9.1.1. Sustained Virologic Response (SVR)

SVR will be based on the standard definition of SVR-12, defined as an undetectable HCV RNA in a subject's serum 12 weeks after completing treatment for HCV (12 weeks after the subject takes the last dose of Zepatier, Epclusa, or another appropriate antiviral treatment).

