Study observations	
 • Laboratory tests including hepatic function panel at screening and at multiple time points during follow-up. • Fibroscan at screening, post-transplant (prior to treating HCV), and post-treatment. • HCV RNA prior to treatment, on treatment, and 4 and 12 weeks after completing Zepatier, Epclusa, or another appropriate antiviral treatment.
Type of control	None
Number of subjects	Estimated 11 HCV-negative subjects transplanted with a lung from an HCV-infected donor
Plan for statistical analysis	Primary endpoint:

	
• Post-treatment sustained virologic response (SVR) 
Secondary endpoints:
 
• Determine if there are major adverse events attributable to HCV therapy in post-lung transplant patients.• Evaluate 1-year lung graft survival in HCV-negative patients who receive a lung transplant from an HCV-positive donor• Determine the rates of spontaneous HCV clearance among HCV-negative patients with lung failure receiving a lung from an HCV-positive donor 
Data analysis:
 
The primary analysis will be based on a calculation of SVR rates (number of subjects with SVR-12; negative HCV RNA 12 weeks after completing Zepatier, Epclusa, or another appropriate antiviral treatment / (number of subjects treated with Zepatier, Epclusa, or another appropriate antiviral treatment post-lung transplantation)

--	---

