7.1.2. Administration of Zepatier

Merck & Co will manufacture, package, and label Zepatier drug. There will be one bottle per subject containing a 28-day supply (28 capsules) of 100/50 mg Zepatier tablets. Daily dose will be one tablet.

The Investigational Drug Services (IDS) pharmacy, directed by [name], will only be required to store and distribute Zepatier. Sofosbuvir and Ribavirin will be purchased and sourced locally. Both of these medications will be purchased and stored by the IDS pharmacy at Penn. Ribavirin will be generic and the manufacturer will vary depending on monthly price fluctuations.

Zepatier will be picked up from the investigational drug services (IDS) pharmacy by the research staff at 28-day intervals. The study staff will deliver the medication to the subjects at their study visits (patients expected to be at home by the time that HCV therapy is initiated and patients will be given medication at their scheduled post-transplant/study visit). Treatment with the study drug will begin within 4 weeks post-transplant. If hepatitis C is not cured after a subject has received Zepatier, he or she will be treated with a second regimen that includes Zepatier plus Sovaldi (Sofosbuvir) and Ribavirin. Any patient (male or female) receiving ribavirin as part of the first- or second-line regimen will be required to use two methods of birth control while on Ribavirin therapy, with continuing two forms of birth control for up to 6 months after the last dose of the study drug.

If patients have baseline NS5A drug resistance assay testing that demonstrates polymorphisms at positions M28, Q30, L31, and/or Y93, treatment with Zepatier will be extended to 16 weeks, rather than 12 weeks, and renally-adjusted Ribavirin at the clinician's discretion will be initiated, and continued for the remainder of therapy (until the 16 week mark). Such a strategy will provide optimal treatment, without delaying therapy prior to receipt of results of NS5A drug resistant testing.

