7.1.5. Zepatier Initial Treatment Failures

Study subjects with treatment failure, defined as virologic breakthrough (when an undetectable viral load while on treatment becomes detectable) or virologic relapse (undetectable viral load after completion of Zepatier treatment that during the 12-week post-treatment follow-up period becomes detectable) will be provided open-label Zepatier + Sofosbuvir (Sovaldi) 400 mg + Ribavirin (generic), renally dosed based on creatinine clearance per the manufacturer guidelines. Any subjects who experience treatment failure will repeat the original study lab visit and visit protocol once they begin their secondary treatment with Zepatier, sofosbuvir, and ribavirin, similar to subjects initiating HCV treatment following lung transplantation. Prior to initiating treatment with this regimen, patients will have serum NS5A resistance (RAV) testing.

7.2. Epclusa for lung recipients with genotype 2, 3, 5, or 6 HCV infections

Upon receiving the results of genotype testing of the donor and/or lung recipient showing HCV infection that is neither genotype 1 nor genotype 4 (genotypes 2, 3, 5 or 6), PIs will begin Epclusa that will be locally sourced by the hospital pharmacy. In the unlikely event that the patient has a contraindication to Epclusa, another optimal antiviral regimen will be selected.

The Hospital of the University of Pennsylvania (HUP) will provide the antiviral treatment and coordinate the application to the subjects insurance company for coverage of the antiviral treatment. In the event that the subject's insurance company denies coverage for the antiviral treatment, HUP will provide the entire HCV treatment regimen at no charge to the subject. In the event that the subject fails to be cured of HCV with the initial treatment regimen and the subject's insurance declines to pay for a second antiviral treatment, HUP will provide the second HCV treatment regimen at no charge to the subject.

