8.1.3.11. Additional Visits

Additional visits will only be necessary in the case of treatment failures. If treatment failure occurs, subjects with genotype 1 or 4 infections will be treated with Zepatier and two other hepatitis C medications, Sofosbuvir (Sovaldi), and Ribavirin for an additional 12 weeks. All study and lab visits will be repeated during this secondary treatment period. NS5A resistance (RAV) testing will be checked again (a second time) prior to initiating second-line therapy.

If treatment failure occurs for patients with non-genotype 1 and non-genotype 4 infections (i.e. genotypes 2, 3, 5, or 6), the PIs will evaluate these patients for second treatment regimen that will be paid for either by the patient's insurance company or provided by HUP if the insurance company denies payment.

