10 CHAPTER 7: STATISTICAL CONSIDERATIONS

10.1. Study Design

This open-label trial involves one primary and several secondary objectives. Post-transplant HCV status will be monitored, and patients will be treated with 12-16 weeks of therapy with Zepatier, Epclusa, or another appropriate antiviral treatment, after which time, treatment will be complete, barring instances of treatment failure, which would require an additional course of therapy.*

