10.3. Analyses of Outcome Measures

The primary analysis will evaluate SVR-12 rates of HCV-negative lung transplant recipients who receive a lung from an HCV-infected donor and subsequently develop de-novo HCV. All patients will be assessed for toxicity and included in the safety analysis. This analysis will include summaries of the incidence and grade of toxicities. Patients will be evaluated for serious adverse events. Safety interim analyses will be performed and reported at each DSMB meeting.

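### Could a subject cured only on retreatment count as a success in the primary SVR-12 rate?

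*Combined protocol and SAP*

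**What the plan says.** Section 9.1.1 adopts the standard SVR-12, undetectable HCV RNA at "12 weeks after the subject takes the last dose of Zepatier, Epclusa, or another appropriate antiviral treatment". The synopsis gives the numerator as subjects with "negative HCV RNA 12 weeks after completing Zepatier, Epclusa, or another appropriate antiviral treatment" and the denominator as subjects treated. Section 10.3 adds no limit: "The primary analysis will evaluate SVR-12 rates of HCV-negative lung transplant recipients who receive a lung from an HCV-infected donor".

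Retreatment is part of the protocol. Section 7.1.2: "If hepatitis C is not cured after a subject has received Zepatier, he or she will be treated with a second regimen". Section 7.1.5 gives that regimen as Zepatier with sofosbuvir and ribavirin, and says these subjects "will repeat the original study lab visit and visit protocol once they begin their secondary treatment with Zepatier, sofosbuvir, and ribavirin". Section 8.1.3.11 adds: "All study and lab visits will be repeated during this secondary treatment period". Section 10.1 says that after 12 to 16 weeks "treatment will be complete, barring instances of treatment failure, which would require an additional course of therapy".

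No sentence states that a retreated subject is a non-responder in the primary analysis.

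**The concern.** Read alone, 9.1.1 does not say which course the last dose belongs to. A genotype 1 or 4 subject who relapses and is retreated takes a last dose of Zepatier in the second course. Undetectable RNA 12 weeks after that dose fits the sentence. Section 10.1 can be read as supporting this, since it makes completion conditional on there being no failure.

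If that reading were used, the headline figure could mean either SVR after the initial regimen or cure after up to two courses. The trial is open-label and uncontrolled, so the choice could be made with the results in view. With 11 subjects a single reclassified case is visible in the estimate. Neither the intent-to-treat statement in 10.5 nor the completers analysis in 10.4 settles it, because those rules govern who is counted and not which course's result is used.

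**Working it through.** The plan gives no power, null rate, threshold or precision target for the 11 subjects, so there is no stated figure to reproduce. The main check is on the text; the arithmetic only sizes the alternative reading.

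**1. Which course does the text mean?**

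- *Completion.* The Study design row of the synopsis ends Zepatier treatment at 12 weeks, with a planned 16-week exception for NS5A variants. The numerator, in the same synopsis, counts from completion.
- *Failure.* Section 7.1.5 defines relapse as RNA that becomes detectable again after Zepatier treatment has been completed, within the 12-week follow-up. A relapser has therefore completed treatment and then failed, in the same window that SVR-12 measures. This goes against the inference from 10.1 that a failing subject has not yet completed. Section 10.1 itself calls retreatment an additional course, that is, additional to the 12 to 16 weeks.
- *Order of events.* In 7.1.2 the judgement that the subject is not cured comes before the second regimen and triggers it.
- *Schedule.* Section 8.2.1 has one SVR 12 row, at week 24 after transplant. The first course ends at week 13 in that table, so the row is timed to the first course. Section 8.1.3.3.1 moves procedures by 4 weeks for the 16-week course.
- *Risk sections.* Section 12.11.3 speaks of failing first-line therapy and then needing second-line therapy. Section 12.11.4 names failure to reach SVR12 after Zepatier as the greatest risk. Both treat SVR-12 as the outcome of the initial regimen.

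**2. Would a second SVR-12 reading exist?**

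Assume treatment starts at week 1 to 4, relapse is seen 4 to 12 weeks after the course ends, and a 12-week retreatment starts at once.

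- 12-week first course: earliest 1 + 12 + 4 + 12 + 12 = week 41; latest 4 + 12 + 12 + 12 + 12 = week 52.
- 16-week first course: earliest week 45, latest week 56.

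A reading could mostly fall inside the 52-week follow-up. That it would be taken is inferred from the repeated visit schedule. Section 8.1.3.11 repeats visits only during the second treatment period, and no section names a second SVR-12.

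**3. Size if retreated cures were counted (n = 11)**

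Exact (Clopper-Pearson) 95% intervals:

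| Rescued failures | First course only | Any course |
|---|---|---|
| 1 | 10/11 = 90.9% (58.7 to 99.8) | 11/11 = 100% (71.5 to 100) |
| 2 | 9/11 = 81.8% (48.2 to 97.7) | 11/11 = 100% (71.5 to 100) |

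Let p be the true first-course SVR, taken over the 94 to 100% range quoted in 4.3 and 7.1. Let s be the second-line cure rate, assumed to be 50 to 90% because the documents give none. Assume also that all 11 are genotype 1 or 4 and all failures are retreated.

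- At least one failure, 1 − p^11: 49% at p = 0.94; 28% at 0.97; 0% at 1.
- At least one rescued failure, 1 − [1 − (1 − p)s]^11: 28% to 46% at 0.94; 15% to 26% at 0.97; 0% at 1.
- Expected upward shift, (1 − p)s: 3.0 to 5.4 points at 0.94; 1.5 to 2.7 at 0.97; 0 at 1.

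The intervals themselves are 100 − 71.5 = 28.5 and 99.8 − 58.7 = 41.1 points wide.

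**The case for a change.** The best case for a change is that signs of intent are not a rule. None of the sections that point to the first course is tied to the numerator. The one sentence that defines the endpoint can be met by a second course containing Zepatier, and the fix would be one sentence with no effect on treatment or visits. The 9.1-point step is correct, and at a true rate of 94% a first-line failure is about as likely as not.

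Part of this stands. The wording is open if read in isolation. Section 7.1.5 does not list a subject who never becomes undetectable among its failures. A subject with breakthrough may move to the second regimen before the first course is finished, so the argument from completion is weaker there than for relapse; the failure label in 7.1.5 has to carry that case.

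Two supports for the objection are weaker than they look. The 94 to 100% range is not described as a first-course benchmark: one of the two references cited for it is, by its title, a study of patients in whom earlier direct-acting antiviral combinations had failed. The range is also background and not a planned comparator. And the expected shift needs an assumed second-line cure rate, an inferred second sample and the less natural reading of the text, all at once.

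**Conclusion.** No change follows. The plan leaves a counting rule unsaid, but its own definitions of completion and failure, its single SVR 12 time point and its separation of first-line from second-line therapy lead an analyst to first-course SVR, with a retreated relapse or breakthrough counted as not achieving it. An added sentence would record that rule without altering the analysis.

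The 9.1-point step per subject would arise only if a failure occurred, was rescued, was sampled again 12 weeks after retreatment, and was then scored against the protocol's own failure label. No expected bias should be claimed from the 0 to 5.4 point range, which depends on the assumed second-line cure rate of 50 to 90% and on every subject being genotype 1 or 4. The analysis is descriptive in a pilot of 11, with no test or success threshold that the choice could tip. Retreatment would be visible from the repeated visits, so a reader of the results could see any failure behind the rate.

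The conclusion rests on reading 9.1.1 together with the synopsis and Sections 7.1.5, 8.2.1, 12.11.3 and 12.11.4. It would be weaker if 9.1.1 were the only text on the endpoint.

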9.2. Secondary Outcome Measures

- To determine safety of administering Zepatier, Epclusa, or another appropriate antiviral treatment to lung transplant recipients who were previously HCV-negative, but developed de-novo HCV after receiving a lung transplant from an HCV-infected donor
- To determine 1-year graft survival rates of HCV-negative lung transplant patients who receive a lung transplant from an HCV-infected donor, including those who spontaneously clear HCV and those who receive open-label Zepatier, Epclusa, or another appropriate antiviral treatment upon development of de-novo HCV.
- To evaluate rates of spontaneous clearance of HCV among HCV-negative patients who receive a lung transplant from an HCV-infected donor.

9.2.1. Safety

Subject safety and adverse events will be based in CTCAE Version 4 criteria, listed in Section 13, and will include adverse events and serious adverse events, related both to receipt of a lung transplant from an HCV-positive donor among HCV-negative subjects with lung failure, and adverse events related to administration of Zepatier, Epclusa, or another appropriate antiviral treatment.

9.2.2. Graft Survival

Graft survival will be based on standardize United Network for Organ Sharing (UNOS) criteria, with a graft failure defined as subject death, or re-transplantation within the first year post-transplantation.

9.2.3. Spontaneous Clearance or Non-Transmission of HCV

Spontaneous clearance or non-transmission of HCV will be based on an undetectable HCV RNA level at post-transplant weeks 1-4 in the absence of treatment among HCV-negative subjects who receive a lung transplant from a confirmed HCV-infected donor. Any subject who experiences spontaneous clearance of HCV or non-transmission of HCV will still be tested for HCV RNA at weeks 8, 16, and 28, to ensure that their levels are still undetectable.

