8.1.3.3. Visit 1: Post-Lung Transplant (between days 2 - 7)

The study staff will meet the subject in their HUP hospital room, three days after their lung transplant.

Initiating antiviral treatment

Treatment with the study drug will begin when the patient has a detectable and quantifiable HCV RNA post-transplantation and the donor and/or recipient have had an HCV genotype ascertained to guide treatment. As appropriate, subjects being discharged will be provided with a sufficient supply of the study drug.

As with any scientific protocol, safety will be considered before treating the patients. The treating physician will evaluate the patient's overall condition and make a judgment on whether initiating treatment is safe.

The following research procedures and activities will be performed:

- Assess for Adverse Events
- Obtain medication data
- Research Phlebotomy, including the NS5A drug resistance assay testing as appropriate (See Section 8.2.1 for complete list)
- Dispense study drugs

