8.1.3.4. Visit 2: Post-Lung Transplant (day 10 ± 1 day)

Visit #2 should occur two weeks (10 ± 2 days) after the subject's lung transplant and coincide with the subject's regularly scheduled post-transplant follow-up visit. The staff will call the subject 1-2 days before the visit. During this phone call, the research staff will remind the subject where to go for the study visit, to take their routine and study medications as they usually would prior to the visits and if a fibroscan is needed, inform the subject and remind him/her to not eat or drink for three hours before the study visit.

The subject will arrive at the study site outpatient clinic. The following procedures and activities will be performed:

- Assess for Adverse Events
- Obtain medication data
- Research Phlebotomy (See Section 8.2.1 for complete list)
- Pill count and verbal assessment for drug adherence
- Schedule appointments for follow-up visits

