8.1.3.6. Visit 4 Post-Lung Transplant (day 28 ± 3 days)

Visit #4 should occur 4 weeks (28 ± 2 days) after the subject's lung transplant and coincide with the subject's regularly scheduled post-transplant follow-up visit. The staff will call the subject 1-2 days before the visit. During this phone call, the research staff will remind the subject where to go for the study visit, to take their routine and study medications as they usually would prior to the visits and if a fibroscan is needed, inform the subject and remind him/her to not eat or drink for three hours before the study visit.

The subject will arrive at the study site outpatient clinic. The following procedures and activities will be performed:

- Assess for Adverse Events
- Obtain medication data
- Research Phlebotomy (See Section 8.2.1 for complete list)
- Fibroscan (elastography of liver)
- Health Status Questionnaire (RAND-36) (to assess changes in health status from pre- to post-transplant)
- Pill count and verbal assessment for drug adherence
- Replenish study drug as appropriate with the DAA prescribed from the specialty pharmacy
- Schedule appointments for the follow-up visits

HCV Non-Transmission

It is possible that a subject may not develop chronic HCV infection, either due to non-transmission or spontaneous clearance of HCV by week 4 (defined as an initial positive HCV RNA and subsequent undetectable HCV RNA without treatment). If a subject has an undetectable HCV RNA based on the week 4 HCV RNA, a repeat HCV RNA will be checked at week 8 to ensure non-infection with HCV, rather than a false-negative HCV RNA. If the week 8 HCV RNA confirms lack of infection (undetectable week 8 HCV RNA), then no further treatment will be needed. Subjects will be assessed at a study visit and HCV RNA levels re-checked at week 16 and 28 post-lung transplantation. Should any subject spontaneously clear HCV without treatment, another subject will replace them in order to meet our planned treatment sample size.

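### The outcome rule in section 9.2.3 pools spontaneous clearance with non-transmission and needs no prior positive RNA, so never-infected recipients count toward a clearance-only aim

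*Combined protocol and SAP*

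**What the plan says.** All references are to the combined protocol and SAP.

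**The aim.** The secondary outcome list in section 9.2 reads "To evaluate rates of spontaneous clearance of HCV among HCV-negative patients who receive a lung transplant from an HCV-infected donor", and section 5.2 has the same aim. The synopsis endpoint is "Determine the rates of spontaneous HCV clearance among HCV-negative patients with lung failure receiving a lung from an HCV-positive donor". All three name clearance only, and all take the recipients of infected-donor lungs as the population.

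**The outcome rule.** Section 9.2.3 states: "Spontaneous clearance or non-transmission of HCV will be based on an undetectable HCV RNA level at post-transplant weeks 1-4". It adds that the subject must be untreated and must have received a lung from a confirmed infected donor. Those who qualify are retested at weeks 8, 16 and 28.

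**The other definition.** Section 8.1.3.6, in the text on HCV non-transmission at visit 4, names non-transmission and clearance as two different ways of not developing chronic infection. It describes the second as "spontaneous clearance of HCV by week 4 (defined as an initial positive HCV RNA and subsequent undetectable HCV RNA without treatment". An undetectable week-4 result is to be confirmed at week 8.

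**Analysis.** Chapter 7 describes the SVR-12 and safety analyses. It has no analysis that separates the two events.

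**Drug start.** Section 8.1.3.3 (days 2-7) says "Treatment with the study drug will begin when the patient has a detectable and quantifiable HCV RNA post-transplantation", provided a genotype is known and the treating physician judges it safe. The schedule in 8.2.1 marks the day 2-7 row as the start of treatment. The day-10 visit in 8.1.3.4 already includes "Pill count and verbal assessment for drug adherence". Section 7.1.2 allows a start up to 4 weeks after transplant and expects patients to be at home by then. The synopsis lists "Fibroscan at screening, post-transplant (prior to treating HCV), and post-treatment", but the first post-transplant Fibroscan in 8.1.3.6 and 8.2.1 is at day 28.

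**The concern.** Clearance and non-transmission are different events. Clearance says something about an infected recipient's ability to eliminate the virus. Non-transmission says something about the donor organ and the transfer. A rule that asks only for undetectable RNA without treatment cannot tell them apart, and a recipient who never had virus satisfies it.

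The aim promises clearance, so applying 9.2.3 as written can give a non-zero result made up wholly of people who had nothing to clear. In a trial of about 11 treated subjects, one such person can be the entire reported result.

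The timing of the drug adds a second limit. Clearance can be seen only before the first dose. With a start planned in week 1, a zero or low count would partly reflect how soon drug was given. A reader using the pilot to judge how many infected recipients could go without drug would be misled in either case.

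**Working it through.** **1. Inputs.** The planned number treated is 11 (section 3). Clearers are replaced to keep that number (sections 3 and 8.1.3.6), and more patients may be transplanted if some of the first 11 are not infected (section 6.1). With m never-infected recipients and c untreated clearers, the number transplanted is therefore N = 11 + m + c. The documents give no expected value for m or c, so the values below are assumptions. The plan gives no derivation of the 11 and no figure for this outcome, so there is nothing to reproduce.

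**2. The two rules.** Reading 9.2.3 as undetectable by the end of week 4:

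- Section 9.2.3 counts (m + c)/N.
- The 8.1.3.6 definition, over the all-recipient population named in the aim, counts c/N.

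The difference is m/N, one subject in the numerator for each never-infected recipient. With m = 0 the rules agree.

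**3. Numbers.** Intervals are exact (Clopper-Pearson) 95%. For x events in n, the limits are the 2.5% quantile of Beta(x, n - x + 1) and the 97.5% quantile of Beta(x + 1, n - x). For x = 0 the upper limit reduces to 1 - 0.025^(1/n). For n = 12 that is 1 - 0.735 = 26.5%.

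| m | c | N | 9.2.3 rule | 8.1.3.6 definition, all recipients |
|---|---|---|---|---|
| 0 | 1 | 12 | 1/12 = 8.3% (0.2-38.5) | 1/12 = 8.3% (0.2-38.5) |
| 1 | 0 | 12 | 1/12 = 8.3% (0.2-38.5) | 0/12 = 0% (0-26.5) |
| 1 | 1 | 13 | 2/13 = 15.4% (1.9-45.4) | 1/13 = 7.7% (0.2-36.0) |
| 2 | 0 | 13 | 2/13 = 15.4% (1.9-45.4) | 0/13 = 0% (0-24.7) |
| 3 | 0 | 14 | 3/14 = 21.4% (4.7-50.8) | 0/14 = 0% (0-23.2) |

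The first two rows show the problem: 9.2.3 gives the same result for one true clearer as for one person never infected.

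**4. How much clearance can be seen.** The schedule in 8.2.1 has RNA draws through week 4 at days 2-7, 7, 10, 14, 21 and 28. Suppose the first draw is positive, and count the scheduled repeats up to and including a pre-dose draw on the start day:

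- start by day 7: at most 1 (day 7)
- start at day 14: 3 (days 7, 10, 14)
- start at day 28: 5 (days 7, 10, 14, 21, 28)

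The optional viral-kinetics samples in 12.4.4 may add some. The chance to observe clearance therefore varies several-fold with the start day, and the documents do not fix one day.

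**The case against.** The strongest reply is that the protocol already has a sound definition. Section 8.1.3.6 separates the two events, and 9.2.3 itself names both. Calling a never-infected recipient a clearer would contradict 8.1.3.6, and the serial RNA results let anyone separate the events at reporting. The outcome is also secondary, descriptive and untested. Much of this stands: the data are not lacking, and it would be wrong to infer that the protocol never defines clearance. But 8.1.3.6 is a visit procedure, 9.2.3 is the outcome rule, and no text says which governs. Leaving the choice until results are known is avoidable.

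Four stronger readings are tempting and are not supported.

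- *That clearance cannot be observed at all.* The start depends on quantifiable RNA, a genotype and clinical judgement, and 7.1.2 allows up to 4 weeks. Observation is limited, not impossible. Much of the timing text can be reconciled as a trigger, a planned visit and an outer limit, although the Fibroscan and at-home statements still do not fit a week-1 start.
- *That the plan's clearance rate is over infected recipients.* Section 8.1.3.6 gives no denominator, and the aim's population is all recipients. The comparison must be 0/12, not 0/11.
- *That weeks 1-4 means every draw must be undetectable.* A true clearer would then fail the rule. The wording permits this, but it sits badly with the section's title and with the week-4 decision in 8.1.3.6.
- *That a number of missed clearers can be stated.* The documents give no clearance rate, so any such figure would come from assumed rates.

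Section 4.1 mentions a later randomized trial but does not say that this rate feeds its planning, so that consequence is plausible rather than documented.

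**Conclusion.** The point holds. The only outcome rule for a clearance-only aim has a criterion that never-infected recipients meet, and it conflicts with the definition in 8.1.3.6. Each such recipient adds one to the numerator. In the example with 11 treated, 1 never infected and 0 clearers, the reported figure is 8.3% (0.2-38.5%) where clearance is 0/12 (0-26.5%). The intervals overlap heavily, as they must at this size. The defect is in what is counted, not in a significant difference between rates.

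The size rests on an assumed number of never-infected recipients; if there are none, the two rules give the same answer. The conclusion that the rule and the aim do not match needs no assumed rate. SVR-12, whose denominator is treated subjects, is unaffected, as is patient treatment. The change is worth making because it is cheap and settles the definition before results are seen.

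**What to change.** Carry the 8.1.3.6 definition into 9.2.3, align the synopsis, 5.2 and 9.2 with it, and report two counts with exact intervals:

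1. **Non-transmission:** untreated, with no detectable RNA in any sample through the week-8 confirmation, over all recipients.
2. **Spontaneous clearance:** detectable and then undetectable RNA with no antiviral dose given, confirmed undetectable at week 8 and followed by the retests already planned for weeks 16 and 28. Give it over all recipients, the stated population, and also over recipients who were ever RNA-positive.

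The week-8 confirmation matters for the second count. Without it, a passing negative in someone later treated would be scored as clearance. With it, the sum of the two counts may be reported as recipients who needed no drug.

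Keep early treatment. For the second count, list each recipient's untreated days and untreated RNA draws, and state that it is descriptive and not a natural clearance rate. This makes the effect of the start date visible; it does not settle which start rule applies.

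The cost is wording and analysis only. RNA through week 8 and the dosing information come from planned procedures, so no samples, visits or subjects are added. What is given up is a single headline clearance rate.
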